11.0 Treatment Evaluation Using RECIST Guideline

NOTE: This study uses protocol RECIST v1.1 template dated 2/16/2011. See the footnote for the table regarding measurable disease in Section 11.44, as it pertains to data collection and analysis.

Response and progression will be evaluated in this study using the new international criteria proposed by the revised Response Evaluation Criteria in Solid Tumors (RECIST) guidelines (version 1.1) (Eisenhauer et al., 2009). Changes in the largest diameter (unidimensional measurement) of the tumor lesions and the short axis measurements in the case of lymph nodes are used in the RECIST guideline.

- 11.1 Schedule of Evaluations: For the purposes of this study, patients should be reevaluated every 8 weeks.
- 11.2 Definitions of Measurable and Non-Measurable Disease
- 11.21 Measurable Disease
- 11.211 A non-nodal lesion is considered measurable if its longest diameter can be accurately measured as ≥ 2.0 cm with chest x-ray, or as ≥ 1.0 cm with CT scan, CT component of a PET/CT, or MRI.
- 11.212 A superficial non-nodal lesion is measurable if its longest diameter is ≥ 1.0 cm in diameter as assessed using calipers (e.g. skin nodules) or imaging. In the case of skin lesions, documentation by color photography, including a ruler to estimate the size of the lesion, is recommended.
- 11.213 A malignant lymph node is considered measurable if its short axis is ≥ 1.5 cm when assessed by CT scan (CT scan slice thickness recommended to be no greater than 5 mm).
- 11.22 Non-Measurable Disease
- 11.221 All other lesions (or sites of disease) are considered non-measurable disease, including pathological nodes (those with a short axis ≥ 1.0 to < 1.5 cm). Bone lesions, leptomeningeal disease, ascites, pleural/pericardial effusions, lymphangitis cutis/pulmonis, inflammatory breast disease, and abdominal masses (not followed by CT or MRI), are considered as non-measurable as well.
- Note: ‘Cystic lesions’ thought to represent cystic metastases can be considered as measurable lesions, if they meet the definition of measurability described above. However, if non-cystic lesions are present in the same patient, these are preferred for selection as target lesions. In addition, lymph nodes that have a short axis < 1.0 cm are considered non pathological (i.e., normal) and should not be recorded or followed.
- 11.3 Guidelines for Evaluation of Measurable Disease
- 11.31 Measurement Methods:
- All measurements should be recorded in metric notation (i.e., decimal fractions of centimeters) using a ruler or calipers.
 - The same method of assessment and the same technique must be used to characterize each identified and reported lesion at baseline and during follow-up. For patients having only lesions measuring at least 1 cm to less than 2 cm must use CT imaging for both pre- and post-treatment tumor assessments.
 - Imaging-based evaluation is preferred to evaluation by clinical examination when both methods have been used at the same evaluation to assess the antitumor effect of a treatment.
- 11.32 Acceptable Modalities for Measurable Disease:
- Conventional CT and MRI: This guideline has defined measurability of lesions on CT scan based on the assumption that CT slice thickness is 5 mm or less. If CT scans have slice thickness greater than 5 mm, the minimum size for a measurable lesion should be twice the slice thickness.

- As with CT, if an MRI is performed, the technical specifications of the scanning sequences used should be optimized for the evaluation of the type and site of disease. The lesions should be measured on the same pulse sequence. Ideally, the same type of scanner should be used and the image acquisition protocol should be followed as closely as possible to prior scans. Body scans should be performed with breath-hold scanning techniques, if possible.
- PET-CT: If the site can document that the CT performed as part of a PET-CT is of identical diagnostic quality to a diagnostic CT (with IV and oral contrast), then the CT portion of the PET-CT can be used for RECIST measurements and can be used interchangeably with conventional CT in accurately measuring cancer lesions over time.
- Physical Examination: For superficial non-nodal lesions, physical examination is acceptable, but imaging is preferable, if both can be done. In the case of skin lesions, documentation by color photography, including a ruler to estimate the size of the lesion, is recommended.

11.33 Measurement at Follow-up Evaluation:

- In the case of stable disease (SD), follow-up measurements must have met the SD criteria at least once after study entry at a minimum interval of 8 weeks (see Section 11.44).
- The cytological confirmation of the neoplastic origin of any effusion that appears or worsens during treatment when the measurable tumor has met criteria for response or stable disease is mandatory to differentiate between response or stable disease (an effusion may be a side effect of the treatment) and progressive disease.
- Cytologic and histologic techniques can be used to differentiate between PR and CR in rare cases (e.g., residual lesions in tumor types such as germ cell tumors, where known residual benign tumors can remain.)

11.4 Measurement of Effect

11.41 Target Lesions & Target Lymph Nodes

- Measurable lesions (as defined in Section 11.21) up to a maximum of 5 lesions representative of all involved organs, should be identified as “Target Lesions” and recorded and measured at baseline. These lesions can be non-nodal or nodal (as defined in 11.21), where no more than 2 lesions are from the same organ and no more than 2 malignant nodal lesions are selected.

Note: If fewer than 5 target lesions and target lymph nodes are identified (as there often will be), there is no reason to perform additional studies beyond those specified in the protocol to discover new lesions.

- Target lesions and target lymph nodes should be selected on the basis of their size, be representative of all involved sites of disease, but in addition should be those that lend themselves to reproducible repeated measurements. It may be the case that, on occasion, the largest lesion (or malignant lymph node) does not lend itself to reproducible measurements in which circumstance the next largest lesion (or malignant lymph node) which can be measured reproducibly should be selected.
- Baseline Sum of Dimensions (BSD): A sum of the longest diameter for all target lesions plus the sum of the short axis of all the target lymph nodes will be calculated and reported as the baseline sum of dimensions (BSD). The BSD will be used as reference to further characterize any objective tumor response in the measurable dimension of the disease.

- Post-Baseline Sum of the Dimensions (PBSD): A sum of the longest diameter for all target lesions plus the sum of the short axis of all the target lymph nodes will be calculated and reported as the post-baseline sum of dimensions (PBSD). If the radiologist is able to provide an actual measure for the target lesion (or target lymph node), that should be recorded, even if it is below 0.5 cm. If the target lesion (or target lymph node) is believed to be present and is faintly seen but too small to measure, a default value of 0.5 cm should be assigned. If it is the opinion of the radiologist that the target lesion or target lymph node has likely disappeared, the measurement should be recorded as 0 cm.
- The minimum sum of the dimensions (MSD) is the minimum of the BSD and the PBSD.

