11.43 Response Criteria

- 11.431 All target lesions and target lymph nodes followed by CT/MRI/PET-CT/Chest X-ray/physical examination must be measured on re-evaluation at evaluation times specified in Section 11.1. Specifically, a change in objective status to either a PR or CR cannot be done without re-measuring target lesions and target lymph nodes.

Note: Non-target lesions and non-target lymph nodes should be evaluated at each assessment, especially in the case of first response or confirmation of response. In selected circumstances, certain non-target organs may be evaluated less frequently. For example, bone scans may need to be repeated only when complete response is identified in target disease or when progression in bone is suspected.

11.432 Evaluation of Target Lesions

- Complete Response (CR): All of the following must be true:
 - a. Disappearance of all target lesions.
 - b. Each target lymph node must have reduction in short axis to <1.0 cm.
- Partial Response (PR): At least a 30% decrease in PBSD (sum of the longest diameter for all target lesions plus the sum of the short axis of all the target lymph nodes at current evaluation) taking as reference the BSD (*see* Section 11.41).
- Progression (PD): At least one of the following must be true:
 - a. At least one new malignant lesion, which also includes any lymph node that was normal at baseline (< 1.0 cm short axis) and increased to ≥ 1.0 cm short axis during follow-up.

- b. At least a 20% increase in PBSD (sum of the longest diameter for all target lesions plus the sum of the short axis of all the target lymph nodes at current evaluation) taking as reference the MSD (Section 11.41). In addition, the PBSD must also demonstrate an absolute increase of at least 0.5 cm from the MSD.
- Stable Disease (SD): Neither sufficient shrinkage to qualify for PR, nor sufficient increase to qualify for PD taking as reference the MSD.

11.433 Evaluation of Non-Target Lesions & Non-target Lymph Nodes

- Complete Response (CR): All of the following must be true:
 - a. Disappearance of all non-target lesions.
 - b. Each non-target lymph node must have a reduction in short axis to <1.0 cm.
- Non-CR/Non-PD: Persistence of one or more non-target lesions or non-target lymph nodes.
- Progression (PD): At least one of the following must be true:

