16.4 Supplementary Analysis Plans (includes all secondary and translational goals)

- 16.41 Overall survival (OS) is defined as time from randomization to death due to any cause. OS will be estimated with Kaplan-Meier survival curves and differences between regorafenib arms (A vs. B) tested using log-rank tests, though we note these analyses are not powered for formal non-inferiority assessments. See Section 2.21.
- 16.42 Progression-free survival (PFS) is defined as the time from randomization to the earlier of disease progression or death due to any cause, where progressed disease (PD) is as defined by RECIST 1.1 (see Section 11.0). PFS will be estimated with Kaplan-Meier survival curves and differences between regorafenib arms (A vs. B) tested using log-rank tests, though we note these analyses are not powered for formal non-inferiority assessments. See Section 2.21.
- 16.43 Time to progression (TTP) is defined as the time from randomization to disease progression, where progressed disease (PD) is defined by RECIST 1.1 (see Section 11.0). TTP will be estimated with Kaplan-Meier survival curves and differences between regorafenib arms (A vs. B) tested using log-rank tests, though we note these analyses are not powered for formal non-inferiority assessments. See Section 2.21.
- 16.44 The cumulative (total) dose of regorafenib received by patients and dose intensity in the first two cycles will be summarized with descriptive statistics and compared between regorafenib arms (A vs. B) using the t-test (if approximately normally distributed) or the Wilcoxon rank sum test (if not approximately normally distributed). Dose intensity is defined as the cumulative (total) dose of regorafenib divided by the expected total dose. See Section 2.22.
- 16.45 The proportion of patients overall and within each arm experiencing grade 3 or 4 HFS or fatigue will be computed with 95% confidence intervals, and differences between regorafenib dosing strategies (pooled across HFS strategies) tested using a Fisher Exact test. The incidence of grade 3 or 4 HFS will also be descriptively compared between those receiving a pre-specified preemptive vs. reactive approach for hand and foot syndrome (pooled across dosing strategies), and tested using a Fisher Exact test. See Section 2.24. Adverse event reports will be shared with [name] of Memorial Sloan Kettering Cancer Center 1-2 times per month for review.

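### Section 11.41 does not say which post-baseline sum enters the MSD; read with 11.432 as written, target-lesion progression is judged against baseline rather than the smallest earlier sum

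*Combined protocol and SAP*

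**What the plan says.** Section 11.41 (Target Lesions & Target Lymph Nodes) defines three sums. The BSD is the baseline sum. The later sum "will be calculated and reported as the post-baseline sum of dimensions (PBSD)", with nothing to say whether this means the present scan, any one scan or all scans so far. The third is the reference value: "The minimum sum of the dimensions (MSD) is the minimum of the BSD and the PBSD".

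Section 11.432 (Evaluation of Target Lesions) uses these sums as follows.

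- PR is a fall of at least 30% from the BSD.
- PD by target lesions requires "At least a 20% increase in PBSD", where the PBSD is explained in parentheses as the sum "at current evaluation) taking as reference the MSD (Section 11.41)". That relative threshold is paired with an absolute one, under which "the PBSD must also demonstrate an absolute increase of at least 0.5 cm from the MSD".
- SD is "Neither sufficient shrinkage to qualify for PR, nor sufficient increase to qualify for PD taking as reference the MSD".

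Section 16.42 defines PFS by progression "where progressed disease (PD) is as defined by RECIST 1.1 (see Section 11.0)", and 16.43 defines TTP in the same way. The opening of Section 11.0 names RECIST 1.1 as the governing criteria. Section 11.1 and the test schedule in Section 4.0 place tumor assessments every 8 weeks.

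**The concern.** A progression rule needs a fixed reference from an earlier scan. Here the reference is a two-term minimum, and one of its terms is the quantity being tested. If the PBSD means the same thing in 11.41 as in 11.432, the reference moves down with the current sum whenever that sum is below baseline, and an earlier low point plays no part.

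At stake is the progression date in patients whose tumors shrank and then regrew. PFS and TTP (2.21, 16.42, 16.43) and the correlation of PK with PFS (2.33) all use that date. The treatment-end provisions in 13.4 and 13.6 also refer to progression. Two people applying Section 11 in good faith to the same scans, one taking the formula literally and one using the smallest sum on study, could record different dates.

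**Working it through.** The plan states no figure that depends on this definition, so there is nothing to reproduce. The check is algebra plus worked sequences.

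**Inputs.** MSD = min(BSD, PBSD), from 11.41. PBSD = sum at the current scan, from 11.432. PD thresholds of 20% and 0.5 cm above the MSD, and a PR threshold of 30% below the BSD, from 11.432. Scans every 8 weeks, from 4.0 and 11.1. The centimeter values below are illustrative; they are not in the documents.

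**Step 1: the rule as written.** Let B be the baseline sum and C the current sum, so MSD = min(B, C).

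- If C ≤ B, then MSD = C and the increase is (C − C)/C = 0%. PD by target sum is impossible.
- If C > B, then MSD = B and the increase is (C − B)/B.

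So PD by target sum occurs if and only if C ≥ 1.2 × B and C − B ≥ 0.5 cm. That is a baseline-only rule, and the MSD adds nothing to the BSD. A simulation of 20,000 four-scan sequences (assumed lognormal steps with SD 0.2) gave 0 disagreements between the formula as written and the baseline-only rule.

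**Step 2: compare with the smallest earlier sum.** Status at the last scan, by target sum only:

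| Sums (cm) | As written: reference, change, status | Smallest earlier sum: reference, change, status |
|---|---|---|
| 10.0 → 8.5 → 10.5 | 10.0, +5.0%, SD | 8.5, +23.5% and +2.0 cm, PD |
| 10 → 8 → 9.8 | 9.8, 0%, SD | 8, +22.5% and +1.8 cm, PD |
| 10 → 6 → 7.5 | 7.5, 0%, SD | 6, +25% and +1.5 cm, PD |
| 10 → 5 → 6.5 | 6.5, 0%, PR | 5, +30% and +1.5 cm, PD |
| 10 → 8 → 12 | 10, +20%, PD | 8, +50% and +4.0 cm, PD |
| 10 → 12 | 10, +20%, PD | 10, +20% and +2.0 cm, PD |

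First row: 10.5/10.0 = 1.05 and 10.5/8.5 = 1.235. The fourth row stays PR as written because 6.5 cm is still 35% below baseline.

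**Step 3: how far regrowth must go.** Take a baseline of 10.0 cm and a 30% response to 7.0 cm. Against the earlier minimum, PD is reached at 1.2 × 7.0 = 8.4 cm. As written it is reached at 1.2 × 10.0 = 12.0 cm, and 12.0/7.0 = 1.714, a regrowth of 71% rather than 20%. With scans 8 weeks apart, a call missed at one scan moves the target-lesion PD date by at least one 8-week interval.

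**Step 4: which scans.** At the first post-baseline scan the only earlier sum is baseline, so both readings use B. They agreed in all 20,000 simulated sequences at that scan. It falls at week 8 and is the only scheduled post-baseline scan before cycle 3 begins. The readings can part only at later scans, and only if an earlier sum was below baseline.

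**The case against.** The strongest reply is that a smallest-on-study reference is what the protocol means. The restriction to the current scan appears in 11.432, not in the MSD sentence, and can be read there as merely identifying which sum is under test. The name of the MSD points to a minimum over time. PR is referred to the BSD and PD to the MSD, and that separation is pointless if both come down to baseline. Section 11.0, 16.42 and 16.43 commit to RECIST 1.1, and the footnote in 11.44 shows the template being adjusted to match it. No passage excludes earlier sums.

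This stands as evidence of intent, and it rules out one tempting inference: that the sponsor deliberately chose a baseline reference. It does not repair the text. The only place that says which PBSD is meant points to the current scan. The PFS and TTP definitions send the reader back to Section 11.0, where the formula sits. No passage mentions a nadir or all sums to date.

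Two further objections also stand. Even on the literal reading, regrowth is not always called SD: it is PR while still at least 30% below baseline, and PD once 20% (and 0.5 cm) above baseline. New lesions, unequivocal non-target progression and symptomatic deterioration (11.432, 11.433, 11.44, 11.45) still give PD whatever the target sum does. Second, PFS and TTP are secondary, and 16.42 and 16.43 acknowledge that these comparisons lack the power for a formal non-inferiority claim.

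**Conclusion.** The definition is defective as written, with limited reach. Sections 11.41 and 11.432 read together give a baseline-only PD test for target lesions. Followed literally, that test dates progression late in patients who shrank and then regrew, by one or more 8-week intervals where no other route to PD comes first.

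The scope is PD by target-lesion sum, at scans after week 8, in patients with an earlier fall in their sum. The documents do not say how many patients that is, so no overall effect on median PFS or TTP can be stated.

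A reader might infer more than this, and the documents do not support it:

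- **The primary endpoint is compromised.** It is not, in any material way: starting cycle 3 follows the week-8 scan, where both readings agree.
- **OS is affected.** It is not defined by progression.
- **The comparison of arms A and B is biased.** The same rule applies to both arms, and nothing in the documents shows that it acts differently in one.
- **The nadir will in fact go unused in this trial.** The text permits that reading; it does not show what sites or the data-capture system do.

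The conclusion rests on giving the PBSD one meaning in both sections. If 11.41 was meant to cover all post-baseline sums, the practice may already be sound and only the wording needs correcting.

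**What to change.** Reconcile 11.41 with 11.432 by replacing the MSD sentence with: *The MSD is the smallest of the BSD and all PBSDs recorded at evaluations before the current one.* Keep the 11.432 description of the PBSD as the sum at the current scan. Use this reference when PD is derived for PFS and TTP, and check that any calculation in data capture or analysis programs follows it.

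The cost is one sentence and one programming check, with no added patients, visits or scans. PFS and TTP may be slightly shorter than under the literal formula. If the smallest sum is already used in practice, the change only records it.

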11.42 Non-Target Lesions & Non-Target Lymph Nodes

Non-measurable sites of disease (Section 11.22) are classified as non-target lesions or non-target lymph nodes and should also be recorded at baseline. These lesions and lymph nodes should be followed in accord with 11.433.

11.43 Response Criteria

- 11.431 All target lesions and target lymph nodes followed by CT/MRI/PET-CT/Chest X-ray/physical examination must be measured on re-evaluation at evaluation times specified in Section 11.1. Specifically, a change in objective status to either a PR or CR cannot be done without re-measuring target lesions and target lymph nodes.

Note: Non-target lesions and non-target lymph nodes should be evaluated at each assessment, especially in the case of first response or confirmation of response. In selected circumstances, certain non-target organs may be evaluated less frequently. For example, bone scans may need to be repeated only when complete response is identified in target disease or when progression in bone is suspected.

11.432 Evaluation of Target Lesions

- Complete Response (CR): All of the following must be true:
 - a. Disappearance of all target lesions.
 - b. Each target lymph node must have reduction in short axis to <1.0 cm.
- Partial Response (PR): At least a 30% decrease in PBSD (sum of the longest diameter for all target lesions plus the sum of the short axis of all the target lymph nodes at current evaluation) taking as reference the BSD (*see* Section 11.41).
- Progression (PD): At least one of the following must be true:
 - a. At least one new malignant lesion, which also includes any lymph node that was normal at baseline (< 1.0 cm short axis) and increased to ≥ 1.0 cm short axis during follow-up.

- b. At least a 20% increase in PBSD (sum of the longest diameter for all target lesions plus the sum of the short axis of all the target lymph nodes at current evaluation) taking as reference the MSD (Section 11.41). In addition, the PBSD must also demonstrate an absolute increase of at least 0.5 cm from the MSD.
- Stable Disease (SD): Neither sufficient shrinkage to qualify for PR, nor sufficient increase to qualify for PD taking as reference the MSD.

11.433 Evaluation of Non-Target Lesions & Non-target Lymph Nodes

- Complete Response (CR): All of the following must be true:
 - a. Disappearance of all non-target lesions.
 - b. Each non-target lymph node must have a reduction in short axis to <1.0 cm.
- Non-CR/Non-PD: Persistence of one or more non-target lesions or non-target lymph nodes.
- Progression (PD): At least one of the following must be true:
 - a. At least one new malignant lesion, which also includes any lymph node that was normal at baseline (< 1.0 cm short axis) and increased to ≥ 1.0 cm short axis during follow-up.
 - b. Unequivocal progression of existing non-target lesions and non-target lymph nodes. (NOTE: Unequivocal progression should not normally trump target lesion and target lymph node status. It must be representative of overall disease status change.)

11.44 Overall Objective Status

The overall objective status for an evaluation is determined by combining the patient's status on target lesions, target lymph nodes, non-target lesions, non-target lymph nodes, and new disease as defined in the following tables:

For Patients with Measurable Disease

Target Lesions & Target Lymph Nodes	Non-Target Lesions & Non-Target Lymph Nodes	New Sites of Disease	Overall Objective Status
CR	CR	No	CR
CR	Non-CR/Non-PD	No	PR
PR	CR Non-CR/Non-PD	No	PR
CR/PR	Not All Evaluated*	No	PR**
SD	CR Non-CR/Non-PD Not All Evaluated*	No	SD
Not all Evaluated	CR Non-CR/Non-PD Not All Evaluated*	No	Not Evaluated (NE)
PD	Unequivocal PD CR Non-CR/Non-PD Not All Evaluated*	Yes or No	PD

Target Lesions & Target Lymph Nodes	Non-Target Lesions & Non-Target Lymph Nodes	New Sites of Disease	Overall Objective Status
CR/PR/SD/PD/Not all Evaluated	Unequivocal PD	Yes or No	PD
CR/PR/SD/PD/Not all Evaluated	CR Non-CR/Non-PD Not All Evaluated*	Yes	PD

*See Section 11.431

** NOTE: This study uses the protocol RECIST v1.1 template dated 2/16/2011. For data collection and analysis purposes the objective status changed from SD to PR in the ACCRU protocol RECIST v1.1 template as of 2/16/2011 and to match RECIST v1.1 requirements.

For Patients with Non-Measurable Disease Only:

Non-Target Lesions & Non-Target Lymph Nodes	New Sites of Disease	Overall Objective Status
CR	No	CR
Non-CR/Non-PD	No	Non-CR/Non-PD
Not All Evaluated*	No	Not Evaluated (NE)
Unequivocal PD	Yes or No	PD
Any	Yes	PD

*See Section 11.431

11.45 Symptomatic Deterioration: Patients with global deterioration of health status requiring discontinuation of treatment without objective evidence of disease progression at that time, and not either related to study treatment or other medical conditions, should be reported as PD due to “symptomatic deterioration.” Every effort should be made to document the objective progression even after discontinuation of treatment due to symptomatic deterioration. A patient is classified as having PD due to “symptomatic deterioration” if any of the following occur that are not either related to study treatment or other medical conditions:

- Weight loss >10% of body weight.
- Worsening of tumor-related symptoms.
- Decline in performance status of >1 level on ECOG scale.

